The Effects of Disconnection and Reconnection of Definitive Abutments on Peri-implant Bone Levels Changes: A 1-Year Split-Mouth Randomized Controlled Clinical Study

This study has been registered in ClinicalTrial.gov ID. NCT04043286

Document Date: Sep 10th, 2024

Abstract

Background: There is evidence suggesting non-removal of a definitive abutment on an implant from the day of surgery helps to preserve the peri-implant marginal bone levels. However, the limited literatures available still contains contradictory conclusions to this finding.

Objective: The aim of this prospective study was to evaluate the effects of definitive abutment connection at the time of implant placement on peri-implant bone levels and soft tissue changes in posterior maxilla and mandible regions.

Materials and Methods: A total of 38 implants were placed in 17 patients with at least 2 missing posterior teeth in the maxilla or the mandible for this study. Each patient received 2 or 4 implants. A definitive prefabricated abutment (test group) was randomly connected to one implant at implant placement (T0) and left undisturbed throughout the duration of the study. On the other implant, a healing abutment (control group) was connected and subjected to go through three disconnections and reconnections at 3 months (T3), 6 months (T6), and 12 months (T12) after the implant placement. Throughout the study period (1 year), all implants remained unrestored. Marginal bone level changes (MBLC) were assessed using standardized periapical radiographs taken at T0 and T12. Peri-implant soft tissue parameters including the keratinized mucosa width and lingual mucosa thickness were also recorded and evaluated.

Results: At the 1-year follow-up, the test group showed significantly less MBLC compared to the control group. The mean MBLC in the test group was 0.32 ± 0.47 mm, which was significantly lower than the 0.80 ± 0.92 mm observed in the control group ($p=0.009$). The test group also had a smaller reduction in keratinized mucosa width, with a mean reduction of 0.42 ± 0.42 mm compared to 0.90 ± 0.77 mm in the control group ($p=0.049$). Lingual mucosa thickness changes were 0.38 ± 0.26 mm in the test group and 0.71 ± 0.59 mm in the control

group, but this difference did not reach statistical significance ($p=0.053$). However, a significant correlation was identified between changes in keratinized mucosa width and MBLC in the test group ($p=0.02$).

Conclusion: The results of this study support the hypothesis that connecting a definitive abutment at the time of implant placement results in less MBLC compared to repeated abutment disconnections. Additionally, the test group demonstrated better preservation of peri-implant soft tissue compared to the control group. These findings suggest that the one-abutment-one-time protocol may contribute to improved peri-implant tissue stability.

Keywords: *abutment disconnection-reconnection, one-abutment one-time, definitive abutment, one-time abutment, marginal bone loss*

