2.3 Surgical procedures

At the time of implant surgery, patients were escorted to the operating room at the LLUSD Center for Implant Dentistry. They were instructed to rinse their mouths with 0.12% chlorhexidine gluconate solution for 3 minutes prior to surgery. After being seated, monitors were placed to record blood pressure, pulse rate, and oxygen saturation. The patient's circumoral area was sterilized with a Povidone-Iodine swab (Aplicare, Aplicare Inc., Branford, CT), and the area was then draped for a sterile protocol. Oxygen was provided to the patient through a nasal cannula at a minimum flow rate of 3 liters per minute.

Following the administration of local anesthetic (2% lidocaine with 1:100,000 epinephrine [Dentsply, York, PA, USA]), a surgical stent was used to determine the position of implant placement. Pre-operative keratinized mucosa width was measured and recorded at the center of the future implant placement site with a 1.0 mm marked periodontal probe (Hu-Friedy, Chicago, IL, USA). Crestal and intrasulcular incisions were made using a #15 blade (Miltex, Japan), and a buccal periosteal flap was reflected, leaving the lingual mucosal tissue undisturbed. Lingual mucosal tissue thickness was measured with a 1.0 mm marked periodontal probe from the bone crest at the center of the future implant placement. If indicated, lingual periosteal flap reflection and alveoloplasty were performed with a carbide bur (H21L, Komet, Rock Hill, SC) to level the alveolar ridge prior to implant placement. Osteotomy was performed following the manufacturer's recommendations, using the surgical stent as a guide.

The implants used in this study were 4.3 or 5.0 mm in diameter and at least 8 mm in length. They featured a tapered design with TiUnite surface, symmetric threads, and an internal conical connection (NobelReplace Conical Connection, Nobel Biocare, Yorba Linda, CA, USA). A one-stage implant surgery protocol was followed, and the implants were placed 1 mm subcrestally with a minimum insertion torque of 35 Ncm. The minimum distance

between the implant and the adjacent natural tooth was at least 1.5 mm, and between implants, at least 3 mm.

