At implant surgery, after the connection of healing abutments in the control group and definitive abutments with healing caps in the test group, the flaps were approximated and sutured. The width of the keratinized mucosa was recorded from the mid-buccal aspect of the abutments using a 1.0 mm marked periodontal probe (PCP UNC-15, Hu-Friedy, Chicago, IL, USA). At the 1-year follow-up, measurements were taken at the same location before disconnection and reconnection of the healing abutments and healing caps.

Thickness of lingual mucosa

Lingual mucosa thickness was measured at implant surgery and at the 1-year follow-up appointment. The method used for evaluating lingual mucosa thickness was based on the technique described by Linkevicius et al.⁴⁹ At implant surgery, after crestal and intrasulcular

incisions, the buccal flap was raised while the lingual mucosa was not elevated to ensure direct visibility. Lingual mucosa thickness at each implant site was measured from the bone crest using a 1.0 mm marked periodontal probe (PCP UNC-15, Hu-Friedy, Chicago, IL, USA). At the 1-year follow-up, lingual mucosa thickness was measured from the definitive abutment platform and implant platform after disconnection of the healing cap and healing abutment, respectively.

Modified plaque index (mPLI)

Presence or absence of plaque was assessed and recorded at six sites around each implant (mesiobuccal, mid-buccal, distobuccal, mesiolingual, mid-lingual, and distolingual). Plaque assessment was performed with a periodontal probe following the criteria established by Mombelli et al.⁴⁸ Each site was assigned a score according to the following criteria:

- Score 0: No detection of plaque
- Score 1: Plaque only recognized by running a probe across the smooth marginal surface of the healing abutments or healing caps
- Score 2: Plaque visible to the naked eye
- Score 3: Abundance of soft matter

Modified sulcus bleeding index (mSBI)

The mSBI was evaluated and recorded at the same six sites as described for the mPLI assessment following the criteria established by Mombelli et al.⁴⁸ Each site was assigned a score according to the following criteria:

- Score 0: No bleeding observed when a periodontal probe is passed along the gingival margin
- Score 1: Isolated bleeding spots are visible
- Score 2: Blood forms a continuous red line along the gingival margin

- Score 3: Heavy or profuse bleeding is present

Surgical and prosthetic complications

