2.5 Statistical Analysis

Implant was considered the unit of analysis. MBLC at the mesial and distal aspect of the implant during 1-year follow-up was considered the primary outcome of this study.

Descriptive statistics, including means and standard deviations, were calculated for mesial, distal, and overall MBLC, keratinized mucosa width changes, and lingual mucosa thickness changes across the test and control groups. The Shapiro-Wilk test was used to assess the normality of the data. When the assumption of normality was violated, non-parametric methods were utilized alongside traditional parametric tests. Specifically, paired samples t-tests were used to compare MBLC and soft tissue changes between the two groups.

Wilcoxon signed-rank tests were conducted where normality assumptions were not met.

Correlation analyses were performed to explore relationships between all measured parameters, including MBLC, keratinized mucosa width changes, and lingual mucosa thickness changes. All statistical tests were two-tailed, with a significance level set at $p \leq 0.05$. Statistical analyses were conducted using R Statistics version 4.3.3 (The R Project for Statistical Computing, Vienna, Austria).

REFERENCES

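### The Conclusion claims better soft-tissue preservation in general, but only one of the two soft-tissue comparisons in the Abstract meets the document's own 0.05 level, and only narrowly

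*Combined protocol and SAP*

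**What the plan says.** Section 2.5 gives the decision rule: "All statistical tests were two-tailed, with a significance level set at" p ≤ 0.05. It names marginal bone level change (MBLC) as the primary outcome. Soft-tissue changes are compared by paired t-test, or by Wilcoxon signed-rank test where normality fails.

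The Abstract's Results report two between-group soft-tissue comparisons:

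- Keratinized mucosa width: "The test group also had a smaller reduction in keratinized mucosa width", with p=0.049.
- Lingual mucosa thickness: a numerical difference is given, "but this difference did not reach statistical significance" (p=0.053).

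The Conclusion then says "the test group demonstrated better preservation of peri-implant soft tissue compared to the control group". The sentence names no outcome and does not mention the comparison that missed the level.

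Section 2.4 describes the lingual measurement. At surgery: "Lingual mucosa thickness at each implant site was measured from the bone crest using a 1.0 mm marked periodontal probe". At 1 year: "lingual mucosa thickness was measured from the definitive abutment platform and implant platform after disconnection of the healing cap and healing abutment, respectively".

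**The concern.** The Conclusion treats soft tissue as a single finding and calls it demonstrated. By the document's own rule, the evidence is one outcome just inside the level and one just outside it. Someone who reads only the Conclusion would take a general soft-tissue benefit as established and would not learn that one of the two comparisons missed. Nor can the lingual result be counted as clear directional support, because its 1-year reading starts from a different component in each group.

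**Working it through.** **Step 1: apply the stated rule to the reported results.** The level is from section 2.5; the means, SDs and p-values are from the Abstract's Results. Difference = control mean − test mean.

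| Outcome | Test (mm) | Control (mm) | Difference (mm) | Reported p | p ≤ 0.05? |
|---|---|---|---|---|---|
| Keratinized mucosa width, reduction | 0.42 ± 0.42 | 0.90 ± 0.77 | 0.90 − 0.42 = 0.48 | 0.049 | Yes, by 0.001 |
| Lingual mucosa thickness, change | 0.38 ± 0.26 | 0.71 ± 0.59 | 0.71 − 0.38 = 0.33 | 0.053 | No, by 0.003 |

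One of two comparisons meets the level. The p-values are taken as reported. They cannot be reproduced, because the document gives no paired differences or within-pair correlation and does not say which of the two permitted tests produced each p-value.

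**Step 2: compare with the Conclusion.** The results support a statement about keratinized mucosa width. The Conclusion makes a statement about peri-implant soft tissue. The gap is the lingual outcome, which the Results report as not significant.

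**Step 3: ask whether the lingual outcome can still be counted as support.** The reference points in section 2.4 are:

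| Time | Test | Control |
|---|---|---|
| Surgery | Bone crest | Bone crest |
| 1 year | Definitive abutment platform | Implant platform |

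The definitive abutment sits on the implant, so the two 1-year reference points are separated by the height of the abutment base, which the document does not give. The crest and the implant platform are not the same level either, since section 2.3 says "the implants were placed 1 mm subcrestally". No conversion to a common reference is described.

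The direction of any bias depends on what a change means:

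- If it is a reduction, the higher test reference shortens the 1-year test reading and makes the test-group reduction look larger. That works against the test group.
- If it is an increase, the same shift makes the test-group change look smaller. That would look favourable if a small change is read as preservation.

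The Results call the keratinized-width figures reductions but the lingual figures only changes, so the text does not settle which case applies.

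**The case against.** The strongest reply is that the harm is small. The non-significant result is printed just before the Conclusion, the Conclusion's last sentence is hedged, keratinized width is a genuine soft-tissue outcome that met the level, and both numerical differences are smaller in the test group. All of that stands, and it is why the severity is low. It does not rescue the sentence: the hedge applies to the interpretation that follows, and the factual claim remains unqualified.

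A reader might infer more than the documents support:

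- **That the lingual result shows no effect.** It does not. 0.049 and 0.053 are nearly the same strength of evidence; one simply falls outside the stated rule.
- **That the reference points bias the lingual result in favour of the test group.** The direction is open (step 3). If changes are reductions, the bias runs the other way. No base height is given, so no size can be attached.
- **That confidence intervals can be recovered from the p-values.** This presumes paired t-tests, which are not confirmed, and would only restate the p-values. The presumption also fits poorly. With 38/2 = 19 pairs (assuming every implant is paired) and zero within-pair correlation, the reported means and SDs give p of about 0.028 and 0.039. Reaching 0.049 and 0.053 needs correlations of about −0.33 and −0.22. This shows no error, since a Wilcoxon test is allowed.
- **That keratinized width fails after multiplicity correction.** The document sets no such rule for these outcomes, and the point does not need one.
- **That the test-group correlation (p=0.02) is misreported.** It meets the stated level, and section 2.5 already presents correlations as exploratory. It is a within-group association, so it neither supports nor undermines the between-group claim.

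The count of two covers the Abstract only. Section 2.4 also lists plaque and bleeding indices, for which the available text shows no results.

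**Conclusion.** The concern holds as a point about an overstated conclusion. At the document's own two-sided 0.05 level, one of the two soft-tissue comparisons reported in the Abstract is met (keratinized width, 0.48 mm, p=0.049) and one is not (lingual thickness, 0.33 mm, p=0.053). The general wording is not supported before any further adjustment is considered. This rests only on the reported p-values and the stated level.

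The differing 1-year lingual reference points are a fact of section 2.4 as written and should be disclosed or corrected; nothing is claimed about the size or direction of their effect. Severity is low. The outcomes are not primary, no reported number changes, and the MBLC finding (0.32 vs 0.80 mm, p=0.009) does not depend on any of this.

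**What to change.** Keep the MBLC sentence. Replace the soft-tissue sentence in the Conclusion with, for example:

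> Keratinized mucosa width decreased less in the test group (0.42 vs 0.90 mm; p=0.049, not the primary outcome); the difference in lingual mucosa thickness was not statistically significant (0.38 vs 0.71 mm; p=0.053).

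Add that the 1-year reference point for lingual thickness differed between groups. If the readings were in fact converted to one reference, or section 2.4 misdescribes the measurement, correct section 2.4 and leave that addition out.

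The cost is one rewritten sentence and one check of how lingual thickness was recorded. No new data or analysis is needed. The soft-tissue claim becomes narrower; the MBLC conclusion is unchanged.

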1. INTRODUCTION

The peri-implant mucosal barrier consists of two key components: (i) a junctional epithelium approximately 2 mm, and (ii) a connective tissue compartment about 1–1.7 mm.¹⁻³ During healing, it is hypothesized that the connective tissue adheres to the transmucosal implant components, forming a barrier that inhibits epithelial downgrowth and helps prevent peri-implant bone resorption due to bacterial and mechanical insults.⁴⁻⁷ To preserve the marginal bone level around dental implants, it is important to improve the quality and stability of the connective tissue integration, in addition to utilizing a minimally invasive surgical technique.²

Several factors may influence the connective tissue-implant interface, including the type of implant, initial soft tissue thickness,⁸ depth of implant placement,⁹⁻¹² and the stability of the implant-abutment connection.¹⁰ Additional factors include the size of the microgap at the implant-abutment connection, the material and surface topography of the abutment,¹³⁻¹⁵ abutment height,¹⁶ and the abutment emergence profile.¹⁷ The reaction of peri-implant soft tissue to repeated disturbance, such as disconnections and reconnections of the abutment, has also been shown to impact bone resorption.¹⁸⁻²⁰

Abrahamsson et al¹⁹ were the first to report, in an animal study, that repeated abutment disconnections and reconnections can compromise the mucosal barrier, resulting in approximately 0.7 mm of additional peri-implant bone loss and soft tissue recession. This finding led to the development of the "one-abutment-one-time" (OAOT) concept, which advocates placing a definitive abutment at the time of implant surgery to avoid disrupting connective tissue adaptation during restorative procedures. However, subsequent studies in both animals and humans have produced contradictory results regarding peri-implant bone changes.²¹⁻²³ Human studies by Degidi et al reported a significant reduction in horizontal bone remodeling around subcrestally placed tapered implants when a definitive abutment

was delivered at the time of surgery.^{24,25} Similar studies arrived at the same conclusions for implants placed at both immediate post-extraction sites^{20,26,27} and healed sites.²⁸⁻³³ Other studies, however, demonstrated that peri-implant bone levels did not change significantly.³⁴⁻³⁹ Several reviews and meta-analyses also found a lack of consensus on this topic.^{18,40-42} Two meta-analysis concluded that multiple abutment disconnections significantly affect marginal bone level changes in partially edentulous patients.^{43,44} The evidence on this concept remains controversial due to the wide variation in methodologies employed by the studies and the inclusion of confounding factors that may influence the results.⁴⁵⁻⁴⁷

Marginal bone changes are critical for the long-term assessment and maintenance of dental implants, as they form the basis for implant success criteria and help determine the progression of peri-implant pathology.^{45,46} The present study aimed to evaluate peri-implant bone level changes one year after implant placement with a definitive abutment, before functional loading. The null hypothesis was that there would be no significant difference in peri-implant bone levels between implants with definitive abutments delivered at the time of surgery using the one-abutment-one-time protocol, and those subjected to multiple abutment disconnections and reconnections.

2. MATERIALS AND METHODS

2.1 Sample size

Power analysis was carried out to determine the sample size. A sample size of 38 implants was needed to achieve 80% power to detect a difference between the null proportion of 0.500 at a significance level of 0.05.

2.2 Patient selection

This study was designed as a single-center, prospective, randomized modified split-mouth

clinical trial. It was conducted at the Loma Linda University School of Dentistry (LLUSD) Center for Implant Dentistry, California, United States. The study followed guidelines established by the Loma Linda University Institutional Review Board (IRB No.#5190024) and was approved prior to initiation.

To be included in the study, patients had to meet the following criteria: (i) read, sign, and receive a copy of the informed consent form, including consent for photos; (ii) Male or female with at least 18 years of age with good oral hygiene and good general health; (iii) have a healed site with two or more missing teeth in the maxillary or mandibular posterior region (excluding third molars); (iv) have adequate bone width and height to accommodate at least a 4.3 mm diameter and 8 mm length implant at each site; (v) have at least 8 mm of interocclusal restorative space; and (vi) be willing to participate and attend the planned 1-year follow-up visits before starting the implant restoration procedures.

Patients were excluded if they had the following: (i) history of alcohol or drug dependency, or any medical, physical, or psychological factors that might affect the surgical or prosthodontic procedures and follow-up examinations; (ii) history of radiation therapy to the head and neck region; (iii) history or current habit of smoking; (iv) history or current habit of bruxism; (v) no opposing occluding dentition or prostheses; (vi) need for bone augmentation during implant placement; or (vii) implant insertion torque value <35 Ncm. Each patient received at least two implants in the posterior maxilla or mandible. At implant placement (T0), one implant was randomly selected to receive a definitive prefabricated abutment (test group), which was left undisturbed throughout the study. The other implant received a healing abutment (control group), which underwent three disconnections and reconnections at 3 months (T3), 6 months (T6), and 12 months (T12) after implant surgery. All implants were restored with individual screw-retained crowns after the 1-year study period.

2.3 Surgical procedures

At the time of implant surgery, patients were escorted to the operating room at the LLUSD Center for Implant Dentistry. They were instructed to rinse their mouths with 0.12% chlorhexidine gluconate solution for 3 minutes prior to surgery. After being seated, monitors were placed to record blood pressure, pulse rate, and oxygen saturation. The patient's circumoral area was sterilized with a Povidone-Iodine swab (Aplicare, Aplicare Inc., Branford, CT), and the area was then draped for a sterile protocol. Oxygen was provided to the patient through a nasal cannula at a minimum flow rate of 3 liters per minute.

Following the administration of local anesthetic (2% lidocaine with 1:100,000 epinephrine [Dentsply, York, PA, USA]), a surgical stent was used to determine the position of implant placement. Pre-operative keratinized mucosa width was measured and recorded at the center of the future implant placement site with a 1.0 mm marked periodontal probe (Hu-Friedy, Chicago, IL, USA). Crestal and intrasulcular incisions were made using a #15 blade (Miltex, Japan), and a buccal periosteal flap was reflected, leaving the lingual mucosal tissue undisturbed. Lingual mucosal tissue thickness was measured with a 1.0 mm marked periodontal probe from the bone crest at the center of the future implant placement. If indicated, lingual periosteal flap reflection and alveoloplasty were performed with a carbide bur (H21L, Komet, Rock Hill, SC) to level the alveolar ridge prior to implant placement. Osteotomy was performed following the manufacturer's recommendations, using the surgical stent as a guide.

The implants used in this study were 4.3 or 5.0 mm in diameter and at least 8 mm in length. They featured a tapered design with TiUnite surface, symmetric threads, and an internal conical connection (NobelReplace Conical Connection, Nobel Biocare, Yorba Linda, CA, USA). A one-stage implant surgery protocol was followed, and the implants were placed 1 mm subcrestally with a minimum insertion torque of 35 Ncm. The minimum distance

between the implant and the adjacent natural tooth was at least 1.5 mm, and between implants, at least 3 mm.

In the test group, definitive abutment (On1™ Base, Nobel Biocare, Yorba Linda, CA, USA) was randomly assigned to one of the implants, and were torqued to 35 Ncm as recommended by the manufacturer. A healing cap (On1™ Healing Cap, Nobel Biocare, Yorba Linda, CA, USA) was placed over the definitive abutment. In the control group, conventional healing abutment (Healing Abutment CC, Nobel Biocare, Yorba Linda, CA, USA) were hand-tightened onto another implant. The flaps were approximated to allow for non-submerged healing using resorbable polyglactin sutures (5-0 Vicryl Plus Antibacterial suture; Johnson & Johnson, Somerville, NJ, USA). Bite registration (Regisil, Dentsply Sirona Inc., Charlotte, NC, USA) mounted on a Rinn holder was used to create the custom jig for standardized radiographs. Baseline periapical radiographs were taken at implant placement.

Patients were advised to avoid functioning over the surgical sites for the first 3 weeks. A soft diet was recommended throughout the remaining healing period (16 weeks).

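### Baseline lingual mucosa thickness is read from a bone crest that optional alveoloplasty may then remove, and the analysis does not identify the levelled sites

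*Combined protocol and SAP*

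**What the plan says.** Section 2.3 sets out the surgery in sequence. With only the buccal flap raised, the baseline is taken: "Lingual mucosal tissue thickness was measured with a 1.0 mm marked periodontal probe from the bone crest at the center of the future implant placement". The next step is conditional: "If indicated, lingual periosteal flap reflection and alveoloplasty were performed with a carbide bur". Its stated purpose is "to level the alveolar ridge prior to implant placement". Osteotomy and placement, 1 mm below the crest, follow.

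Section 2.4 (Thickness of lingual mucosa) agrees on the state of the tissue at baseline: "the buccal flap was raised while the lingual mucosa was not elevated to ensure direct visibility". It describes one further reading, at one year. That reading starts from the abutment platform in the test group and from the implant platform in the control group, not from the crest.

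Section 2.5 names mesial and distal MBLC as the primary outcome. It says that "paired samples t-tests were used to compare MBLC and soft tissue changes between the two groups", with the Wilcoxon signed-rank test where normality fails, and it plans correlations among all measured parameters. It mentions neither alveoloplasty nor lingual flap reflection, whether as a recorded variable, a covariate, an exclusion or a sensitivity analysis.

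**The concern.** A change score needs its two readings to refer to a stable reference, or to references whose offset is known. At a levelled site, the crest used at baseline has been cut away before the implant goes in. The platform used at 12 months is then positioned from the lowered crest. The recorded change therefore contains an unknown amount of removed bone as well as any change in the mucosa.

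Three results are exposed: each arm's mean lingual-thickness change, any correlation that uses this change and, if the two sites of a pair were not levelled equally, the paired test-control difference. Pairing within a patient removes what the two sites share, but not a procedure carried out to a different extent at each site. The reported p-value of 0.053 lies close to the 0.05 threshold, so a small offset matters more here than it would elsewhere.

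**Working it through.** **Inputs.** From the abstract: change of 0.38 mm (SD 0.26) in the test group and 0.71 mm (SD 0.59) in the control group, p=0.053, and 38 implants in 17 patients. With one test and one control implant per pair, 38 / 2 = 19 pairs. Not given, and so assumed below: how many sites were levelled, how much bone was removed, and how far the mucosal margin followed the bone.

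**Step 1: error at one levelled site.** Let the baseline reading be t0, the bone removed h, and the fall of the mucosal margin m, between 0 and h. Thickness from the levelled crest is t0 + h − m, so the recorded baseline is too low by h − m. This error is 0 if the mucosa follows the bone fully and h if it does not move.

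**Step 2: the reported difference.** 0.71 − 0.38 = 0.33 mm.

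**Step 3: effect on the paired difference.** If k pairs were levelled at one site only, all in the same arm, the shift is at most k × h / 19.
- h = 1 mm, k = 1: 1/19 = 0.053 mm, so 0 to 0.053 mm; at most 0.053/0.33 = 16% of the reported difference.
- h = 1 mm, k = 3: 3/19 = 0.158 mm; at most 48%.
- h = 0.5 mm, k = 1: 0.5/19 = 0.026 mm.
- h = 2 mm, k = 4: 8/19 = 0.42 mm, the top of the assumed range.

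The sign depends on which arm's site was levelled. If both sites of a pair were levelled equally and the mucosa behaved alike, the shift is zero.

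**Step 4: effect on the arm means.** One implant levelled by 1 mm moves its arm's mean by up to 1/19 = 0.053 mm: 14% of 0.38 or 7% of 0.71. Equal levelling within a pair moves both means, and here it does not cancel.

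**Step 5: scale against sampling error.** If p=0.053 came from a paired t-test on 19 pairs, t = 2.071 on 18 degrees of freedom. The standard error is then 0.33/2.071 = 0.159 mm and the SD of the differences 0.159 × √19 = 0.69 mm. Reaching p=0.05 needs 2.101 × 0.159 = 0.335 mm, only 0.005 mm more than was reported. One pair at 0.026 mm exceeds that gap (SD held fixed), while one pair at 0.053 mm is a third of a standard error.

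The SD is itself uncertain. It implies a within-pair correlation of (0.26² + 0.59² − 0.69²)/(2 × 0.26 × 0.59), about −0.2, and the p-value may have come from the Wilcoxon test instead.

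**Step 6: which other outcomes share the problem.** The baseline radiograph for MBLC is taken at implant placement and measured from the implant platform (sections 2.3 and 2.4), after any levelling. The keratinized mucosa width defined in section 2.4 is read after suturing, also after levelling. Neither baseline refers to a removed crest. The one correlation reported as significant in the abstract (p=0.02) links these two outcomes and does not use lingual thickness.

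**The case against.** A reader might infer that levelling was site-specific and so differed within pairs. The documents do not say so. The text speaks of levelling a ridge, which may have covered both sites, and unequal treatment is only a possibility left open by the conditional wording.

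A reader might also infer a systematic bias between arms. The order of events argues against that. Alveoloplasty comes before placement (section 2.3), and random selection is described at placement (section 2.2). On that order levelling cannot depend on arm. It adds variation that the SD of the paired differences already reflects, and chance imbalance is what the test allows for. Three one-sided pairs would all fall in the same arm with probability 2 × (1/2)³ = 1/4. The documents do not say when allocation was revealed, so this rests on the described order.

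A third inference is that the primary outcome is compromised. The landmark problem does not reach MBLC. What remains is that extra bone surgery might affect remodelling. The only support is a general remark in the introduction that preserving marginal bone calls for improved connective tissue integration "in addition to utilizing a minimally invasive surgical technique". It mentions neither procedure and gives no size.

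Finally, the 12-month landmark differs by arm at every site, so handling levelled sites will not by itself make the change score sound. That is true, but it is a separate issue; this error enters at baseline and can occur in either arm.

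These objections limit the scope. They leave the core intact: at a levelled site the change score spans removed bone, and nothing in the analysis identifies those sites.

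**Conclusion.** The point holds for lingual mucosa thickness change, a non-primary outcome, and for correlations that use it. Under the described sequence the score is wrong at any levelled site unless the mucosa followed the bone fully or a later reading was taken that the documents do not describe.

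The size cannot be determined. For 1 mm removed at one site of one of 19 pairs, the mean difference of 0.33 mm moves by 0 to 0.053 mm in either direction. This could carry the p-value across 0.05, because 0.053 is already so close, but it is small against a standard error of about 0.16 mm. If no site was levelled, the effect is nil. Between arms it should be read as added error and possible chance imbalance.

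**What to change.** From the surgical records, flag each of the 38 implants for alveoloplasty and for lingual flap reflection, and report the counts by arm. State whether thickness was re-read after levelling. Add a sensitivity analysis of lingual-thickness change and its correlations that excludes pairs with a levelled site and no post-levelling baseline.

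A missing baseline cannot be recovered now. Any reading made after lingual reflection would depart from the section 2.4 method, which has the lingual mucosa not elevated, so it should be reported as a different measurement. If the records do not show these procedures by implant, say so as a limitation. Repeating the MBLC comparison without pairs discordant for either procedure is optional.

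The cost is a check of 38 sites and one additional run, with a few pairs lost from a non-primary analysis. If no site was levelled, one sentence saying so settles the point.
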